7. STUDY ENDPOINTS

7.1 Primary Endpoints

- GMC of RVNA on Day 8 after administration.
- The incidence and survival rate of rabies in subjects within 99 days and 1 year after administration.

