8.2.4 Emergency Unblinding

Unless it is necessary to meet medical needs, unblinding of the treatment for subjects isn't allowed without the consent of the Sponsor and the investigators and should be with the recommendation of DSMB. In case of any serious adverse event that requires emergency treatment during the study, emergency unblinding can be performed through IWRS if the investigator believe that it is necessary to learn about the drug group and it is beneficial for the handling of the adverse event. The investigator must enter relevant information into the IWRS, such as the reason(s) for emergency unblinding, and reconfirm the necessity of unblinding prior to emergency unblinding. If possible, every effort should be made to notify the principal investigator, CRA, and relevant personnel of the Sponsor of such unblinding before emergency unblinding, and the specific grouping information of the subject can be obtained only with the approvals of the Sponsor and the principal investigator. If the Sponsor cannot be reached before emergency unblinding, it is necessary to contact the Sponsor, the principal investigator, and the CRA within 24 hours after emergency unblinding. The subject requiring emergency unblinding will be deemed as a drop-out case.

Refer to the separate operation manual for the specific emergency unblinding procedures. Please also refer to the DSMB 14.3 chapter.

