9.4.2 Study Withdrawal

The subjects enrolled in this clinical study are eligible patients with Category III exposure to rabies virus. Each subject who has received wound cleaning and the injection of SYN023 or HRIG should complete subsequent rabies vaccination unless the subject requests to withdraw from the study voluntarily. In principle, the investigators must not suspend the subsequent rabies vaccination for any subject for any reason.

Any subject can stop his/her participation in the trial at any time for any reason. All

subjects should be informed of their right to withdraw from the study at any time, and those subjects who withdraw from the study will not be replaced. The investigators must distinguish those subjects who withdraw from this study due to adverse events from those who withdraw from this study for other reasons.

Withdrawal from the study (drop-out) means that a subject cannot complete the last follow-up as required by the trial protocol for any reason.

The investigators should make every effort to get in touch with those subjects who fail to return for follow-up visits within the specified period of time. After the withdrawal of any subject from the study, the investigators should provide necessary guidance to the subject about his/her clinical conditions, and carry out follow-ups on AE/SAE until the subject has a definite diagnosis/stable condition/full recovery.

All data collected before the date when a subject withdraws from the study/the date when a subject is contacted should be used for analysis, and relevant information about such withdrawal should be recorded in the eCRF, such as whether the subject or an investigator makes the decision of withdrawal and the possible reasons for the withdrawal. For example:

- Serious Adverse Event
- Other adverse events
- Death
- Others (detailed description should be provided)

If a subject withdraws from the study after the injection of the study drug/the first dose of vaccine before the completion of the vaccination with 5 doses of rabies vaccine, an investigator should inform the subject of the risks of his/her withdrawal and give recommendations for subsequent preventive measures.

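### Emergency unblinding makes a subject a drop-out, which can end scheduled rabies, survival and RVNA follow-up in subjects selected by a serious event

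*Protocol*

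**What the plan says.** - **Trigger (Protocol 8.2.4).** "In case of any serious adverse event that requires emergency treatment during the study, emergency unblinding can be performed through IWRS", provided the investigator judges that knowing the allocation is needed and helps in handling the event.
- **Consequence (Protocol 8.2.4).** "The subject requiring emergency unblinding will be deemed as a drop-out case". There is no exception by type of event, or for a subject who is willing and able to keep attending.
- **Meaning of drop-out (Protocol 9.4.2; the Glossary agrees).** "Withdrawal from the study (drop-out) means that a subject cannot complete the last follow-up as required by the trial protocol for any reason".
- **What is kept (Protocol 9.4.2).** "All data collected before the date when a subject withdraws from the study/the date when a subject is contacted should be used for analysis". After withdrawal the investigators are also to "carry out follow-ups on AE/SAE until the subject has a definite diagnosis/stable condition/full recovery".
- **Endpoint at risk (Protocol 7.1).** "The incidence and survival rate of rabies in subjects within 99 days and 1 year after administration". Section 2.1 requires that the SYN023 group have no probable or confirmed case, and 13.8 treats any rabies event in that arm as failure of the study.
- **A second description of the same act (Protocol 14.8).** Individual emergency unblinding must be documented and reported to the sponsor and the review board. Drop-out is not mentioned.
- **SAP.** Section 3.2.1.2 describes rabies incidence and survival by number and percentage, with no rule for drop-outs or for the denominator. Section 2.3.4 plans no general handling of missing data. Under 3.2 the PPS is primary and the SS supportive.

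**The concern.** Breaking the code reveals the allocation. It does not stop a subject from attending visits, giving blood or being traced for survival. Section 8.2.4 nevertheless gives that subject the status of someone who has left the study. Because the code is broken only for a serious event needing emergency treatment, the subjects who receive this status are chosen by something that happened to them after dosing. This is outcome-related loss created by the protocol.

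What is at stake is mainly the clinical co-primary endpoint, which rests on a count of zero in the SYN023 arm and needs complete ascertainment to Day 99 and one year. Protocol 5.1 gives a typical rabies latency of 1 to 3 months and mentions one year, so the period after an early code break is when a case would be expected to appear. Later RVNA samples would be lost as well.

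**Working it through.** The plan states no figure on this point, so the main check is to read the sections against each other. Two situations need to be kept apart.

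| | A. The event that prompts the code break is itself rabies or fatal | B. The code is broken for another serious event, which resolves; rabies or death comes later |
|---|---|---|
| Is the event on record? | Yes. It precedes the code break and is reportable within 24 hours (14.4.1) | The first event is; the later one falls after the drop-out date |
| Does 9.4.2 follow it? | Yes, to diagnosis, stability or recovery | No. That duty ends when the first event is settled |
| Does 9.4.2 keep the data? | Data up to withdrawal, plus the continued event follow-up | Only data from before withdrawal |
| Does it reach the adjudication board (13.8)? | Yes, every suspected or confirmed case goes there | Only if someone learns of it; no scheduled visit is assured |
| Is the subject in the SS (SAP 2.2)? | Yes | Yes, but SAP 3.2.1.2 does not say how an unobserved outcome counts |

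The gap is in column B.

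**A further link.** Section 13.8 lists failure to complete the scheduled vaccinations among the violations that can excuse a SYN023 case, and PPS membership requires the completed schedule (Protocol 13.4, SAP 2.2). Section 9.4.2 expects vaccination to continue unless the subject asks to leave. Section 8.2.4 does not say what its drop-out status means for the remaining visits. If on-study vaccination ended, a SYN023 case could become excusable. These sections must be reconciled.

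**Scale, on stated assumptions.** The documents give neither a rabies rate under prophylaxis nor an emergency-unblinding rate.

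1. *Sensitivity of the criterion.* With 750 planned SYN023 subjects, all of whom stay in the SS once dosed, the Clopper-Pearson 95% intervals are:
   - one case seen: 1/750 = 0.13% (0.003% to 0.74%), criterion not met;
   - the same case unseen: 0/750 = 0% (0% to 0.49%), criterion met.
2. *Expected unseen cases.* Let p be the rabies risk per subject and k the number of SYN023 subjects made drop-outs by unblinding. If these subjects carry the same risk as the others, expected unseen cases are at most k × p. The bound is reached only if all of the risk falls after the code break and no other route finds the case. Per subject (k = 1), for assumed p of 0.05%, 0.1%, 0.2% and 0.4%, this is 0.0005, 0.001, 0.002 and 0.004.
3. *For comparison.* Over the same range the whole arm expects 750 × p = 0.375 to 3 cases. The chance of at least one, 1 − (1 − p)^750, is 31%, 53%, 78% and 95%. Each affected subject therefore accounts for at most 1/750 = 0.13% of expected cases.
4. *RVNA.* The stated requirement for the Day 8 comparison is 16 subjects against 1,000 planned. Losing a few titres has no material effect on that power.

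**The case against.** The strongest reply is that drop-out is not exclusion. No section deletes a drop-out from a numerator or denominator. Data from before withdrawal are used, and follow-up of the serious event runs to a definite diagnosis, which is what decides whether suspected rabies is a case. The SS keeps every randomized and dosed subject, and neither PPS definition names unblinding or drop-out. Every suspected case goes to the adjudication board, and its list of excusing violations includes neither. The DSMB watches deaths and rabies throughout the study (13.7), and families are asked to report deaths (11.11.2).

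All of this stands. A reader might infer from 8.2.4 that rabies and fatal cases are struck from the co-primary endpoint because they are cases, so that one SYN023 failure turns into 0/749. The documents do not support that reading. A result of 0/749 needs a rule that takes the subject out of both numerator and denominator, and there is none. The trigger is also the investigator's need to know the allocation in an emergency, not rabies or death as such.

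The reply does not reach the later event. Following one adverse event until it settles is not rabies and survival follow-up to Day 365, and reports that happen to arrive do not replace scheduled visits. The open-ended list of PPS exclusions and the silence of SAP 3.2.1.2 leave the counting unsettled. The separate unblinding manual cited in 8.2.4 and the DSMB charter might answer this. Neither was available.

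**Conclusion.** The point holds as a gap in follow-up and counting. As written, 8.2.4 can end scheduled rabies, survival and RVNA follow-up in subjects selected by a serious event. Nothing in 9.4.2, 13.8 or the SAP restores that follow-up or says that a later rabies case or death counts. Section 14.8 describes the same unblinding without this consequence.

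The expected effect is small: at most 0.0005 to 0.004 unseen cases per affected SYN023 subject, under an assumed risk of 0.05% to 0.4% that is the same as for other subjects. It deserves attention because a zero-case criterion leaves no margin for one missed case.

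Confidence is high on what the text says and moderate on the consequence, since sites may in practice keep following these subjects. This is a cheap improvement. It is not an error shown to remove cases.

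**What to change.** 1. In Protocol 8.2.4, replace the drop-out sentence with: *Emergency unblinding does not by itself end participation. The subject stays in scheduled follow-up to Day 365 unless consent is withdrawn, and the code break is recorded.*
2. Reconcile 9.4.2, 13.8 and 14.8 with that sentence, so that they agree on the status of an unblinded subject and on what that status means for the remaining visits and for adjudication.
3. In SAP 3.2.1.2, add that rabies and survival outcomes of emergency-unblinded subjects count in the endpoint, including events after unblinding, and name the denominator.

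The cost is one protocol sentence with consistency edits and one SAP line. The visits to Day 365 are already planned. The downside is that a few subjects are followed with their allocation known. That matters little for rabies, death or a titre measured by a blinded laboratory. It matters somewhat more for later judgements of adverse-event causality, where the recorded code break allows those subjects to be identified.

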8.2.5 Regulations on Unblinding

The one-time unblinding method is adopted in this study. Unblinding will be carried out after the completion of the follow-up on Study Day 99 after drug injection, signing and confirmation of the statistical analysis plan and the data review report by all parties and database locking. Unblinding refers to the revelation of the group code corresponding to each random number and the study drug corresponding to each group code. The unblinding documents should be jointly signed by the Sponsor and statisticians.

After data locking and unblinding on Study Day 99, blindness should still be maintained for the investigators responsible for the follow-ups on safety and efficacy analysis (in one year after administration).

8.3 Amendments to the Study Protocol

Any amendment to the study protocol should be discussed with and approved by the

Sponsor. If an agreement is reached on the necessity of any amendment, the Sponsor will make a written record and the revised version of the study protocol will replace the earlier version. All amendments to the protocol need to be submitted to the Institutional Review Board (IRB), and important amendments (such as those that may affect the implementation of the study and the safety of subjects) need to be approved by the IRB. Those amendments to the section of management, which do not affect the design or purposes of the study, or the safety of subjects, should be sent to the IRB for registration or quick review (as required by the IRB). If any amendment to the protocol involves study design, attention should be paid to the revision of the informed consent forms and other relevant forms.

The investigators should be responsible for ensuring that if any amendment needs to be made to the study protocol, such amendment must not be implemented prior to the review and approval of the IRB, unless it is necessary to implement such amendment in order to remove any immediate danger to any subject.

8.4 Study Duration

The study duration for each subject is about 12 months, while the total duration of this study is approximately 22 months.

9. HUMAN SUBJECTS

9.1 Population & Number of Enrolled Subjects for the Study

The population for the study includes all people aged 18 and over, regardless of sex or nation.

Please refer to the section "Sample Size Calculation" for details.

9.2 Inclusion Criteria

- 1) Is age 18 years, on Study Day 1 with legal identification documents, and plan to live in the local administration area during the study;
- 2) Category III rabies exposure within 24 hours before Study Drug receipt ;
- 3) Completed written informed consent process, and signed the informed consent forms;
- 4) Subjects with the ability to understand the study procedure. And agreed to complete all follow-ups;
- 5) Female subjects are not in pregnancy (with negative results of urine pregnancy tests before vaccination) and are not in the period of breast feeding, and agree to avoid pregnancy within 6 months after administration;
- 6) Those who have an armpit temperature $\leq 37.0^{\circ}\text{C}$.

9.3 Exclusion Criteria

- 1) Previous receipt of equine or human (rabies) globulin or rabies vaccination prior to randomization;
- 2) Clinical evidence of rabies infection;

- 3) Category I and Category II rabies exposure ;
- 4) Had fever (armpit temperature $\geq 38.5^{\circ}\text{C}$) within 3 days before Study Day 1, or in the acute episode of any chronic diseases;
- 5) Received immunoglobulin or blood products (except for the anti-tetanus immunoglobulin) within 43 days before Study Day 1, or plan to use any such product (except for the anti-tetanus immunoglobulin) during the study;
- 6) Received systemic immunosuppressant medication such as systemic corticosteroids but not limited to systemic corticosteroids within 43 days before Study Day 1;
- 7) History of any immunodeficiency disease (for example: AIDS, systemic lupus erythematosus, etc.); or Laboratory evidence of previous or current immunodeficiency disease, including, but not limited to, any laboratory evidence of HIV infection;
- 8) History of spleen function deficiency or function injury, such as no spleen caused by any cause (such as splenectomy);
- 9) History of any severe allergy for vaccination, such as systemic urticaria, allergic laryngeal edema, anaphylactoid purpura, local allergic necrosis (Arthus reaction), angioedema, anaphylactic shock, etc., or allergic to any ingredient of the study drug/vaccine;
- 10) Previous receipt of any study product (drug, vaccine, biological product or device) within 6 months before Study Day 1, or plan to participate in any other clinical study during this study period;
- 11) History of or clinical evidence of any systemic disease, acute disease or chronic disease (such as convulsions, epilepsy, encephalopathy, nephrotic syndrome, etc.) that the investigator considers to be likely to interfere with safety or efficacy assessment of the study;
- 12) Previous medical history that may compromise the safety of the subject in the study according to the opinion of the principal investigator.

9.4 Study Completion and Withdrawal

9.4.1 Study Completion

Those subjects who have completed all visits as required by the protocol should be deemed to have completed the study.

9.4.2 Study Withdrawal

The subjects enrolled in this clinical study are eligible patients with Category III exposure to rabies virus. Each subject who has received wound cleaning and the injection of SYN023 or HRIG should complete subsequent rabies vaccination unless the subject requests to withdraw from the study voluntarily. In principle, the investigators must not suspend the subsequent rabies vaccination for any subject for any reason.

Any subject can stop his/her participation in the trial at any time for any reason. All

subjects should be informed of their right to withdraw from the study at any time, and those subjects who withdraw from the study will not be replaced. The investigators must distinguish those subjects who withdraw from this study due to adverse events from those who withdraw from this study for other reasons.

Withdrawal from the study (drop-out) means that a subject cannot complete the last follow-up as required by the trial protocol for any reason.

The investigators should make every effort to get in touch with those subjects who fail to return for follow-up visits within the specified period of time. After the withdrawal of any subject from the study, the investigators should provide necessary guidance to the subject about his/her clinical conditions, and carry out follow-ups on AE/SAE until the subject has a definite diagnosis/stable condition/full recovery.

All data collected before the date when a subject withdraws from the study/the date when a subject is contacted should be used for analysis, and relevant information about such withdrawal should be recorded in the eCRF, such as whether the subject or an investigator makes the decision of withdrawal and the possible reasons for the withdrawal. For example:

- Serious Adverse Event
- Other adverse events
- Death
- Others (detailed description should be provided)

If a subject withdraws from the study after the injection of the study drug/the first dose of vaccine before the completion of the vaccination with 5 doses of rabies vaccine, an investigator should inform the subject of the risks of his/her withdrawal and give recommendations for subsequent preventive measures.

9.4.3 Handling of Missing Visits

If a subject cannot return to the site for a follow-up examination on time, the investigators should make efforts to contact the subject to make a confirmation or recall the subject, or at least determine the subject's health status, and record such efforts (such as, phone call and SMS records).

9.5 Deviation From/Violation against the Protocol

Deviation from the protocol: refers to any behavior that does not conform to the clinical study protocol design or process and hasn't been approved by the Institutional Review Board. A behavior that does not affect the rights, safety and benefits of the subjects, or the integrity, accuracy and reliability of the study data and the evaluation of safety or main indexes should be deemed as a minor deviation from the protocol; a behavior that affects the rights, safety and

benefits of the subjects, or the integrity, accuracy and reliability of the study data and the evaluation of safety or main endpoints should be deemed as a serious deviation from the protocol (violation against the protocol).

It is unnecessary to report minor violation against the protocol (i.e., a deviation from the protocol), such as that the fifth dose of vaccine isn't injected within the window period, to the Institutional Review Board.

The on-site investigators should report to the principle investigator's unit, the Sponsor, the Institutional Review Board, and the Clinical Monitoring about the fact, process, cause, and impact of any serious deviation from the protocol (violation against the protocol) that occurs during the study process. The principal investigator and the Sponsor should give their opinions on the handling of such deviation.

The investigators should provide a corresponding training on relevant procedures to those personnel involved in any violation against the protocol in order to prevent similar incidents from happening again, and should record the training process.

9.6 Pregnancy-related Events

Pregnancy is a criterion of exclusion for subject enrollment, so female subjects are required to take effective contraceptive measures during the study; however, they may still get pregnant unexpectedly during their participation in this study. All pregnancy-related events of the subjects during the study period should be reported, and investigators should fill in the "Pregnancy-related Event Report Form".

Investigators should conduct close follow-up on any pregnant subject and collect information about the outcome of pregnancy (for example, detailed information about childbirth, conditions of the newborn baby or termination of pregnancy), and update the "Pregnancy-related Event Report Form".

The starting date of pregnancy should be the first day of the last menstruation.

Pregnancy shouldn't be considered as an adverse event/serious adverse event, but any complication that occurs during pregnancy will be considered as an adverse event, and will even be considered as a serious adverse event in some cases, such as: spontaneous abortion, fetal death, stillbirth, and congenital abnormalities. If no abnormality is found in the fetus, and the mother decides to have induced abortion, such event should not be considered as an adverse event.

9.7 Study Suspension/Termination

In case of any of the following circumstances, the trial needs to be suspended, and the circumstance should be reported to the Institutional Review Board and the drug authorities in

accordance with relevant regulations. An expert meeting will be held for safety demonstration. If necessary, earlier unblinding can be performed in order to determine whether the trial should be continued:

- When any subject dies or experiences any serious life-threatening adverse reaction related to the study drug during the study;
- When the number of subjects with Grade 3 or higher-grade systemic adverse reactions accounts for 20% or more of the number of subjects taking the study product during the follow-up period

If the study is terminated early or suspended, the Sponsor will notify the investigators, the Institutional Review Board, and the drug authorities of the reason for the suspension or termination immediately in accordance with relevant registration regulations.

Regardless of the reason for the early termination of the study, the investigators should notify all subjects immediately of such termination and carry out appropriate follow-up visits on the conditions of the subjects.

10. Study Drug/Control and Vaccine in combination

